- Peripheral neuropathy
- Inflammatory bowel diseases
- Intestinal occlusion
- Chronic liver disease (viral, alcoholic or metabolic)
- Immunodeficiency syndromes (transplant history, HIV infection)
- Known contraindications to 5FU, oxaliplatin, folinic acid, irinotecan or contrast media
- Patient with known contraindication to liver embolization procedures:
 - Presence of bilio-digestive anastomoses or biliary prosthesis
 - Cruciate or tumor thrombosis of the portal vein
- Patient who for psychological, social, family or geographical reasons could not be followed regularly
- Legal incapacity (persons deprived of liberty or under guardianship)
- Patient not affiliated with a social security plan.
- Concurrent participation in another study investigating the effect of a treatment until 4 weeks after the end of this study.

III. PRE-INCLUSION ASSESSMENT

To be performed within 21 days prior to treatment and before inclusion:

- Thoracoabdomino-pelvic CT scan, documenting at least one measurable liver lesion
- Hepatic MRI
- PET scan strongly recommended before inclusion.

Remember to keep the radiology CDs in the patient's file; the ARC FFCD will make a copy of these imaging studies.

To be completed within 14 days prior to inclusion:

- Complete clinical examination including: weight, height, vital signs, WHO index, pain assessment (VAS)
- Medical history
- Description of the disease
- Biological workup consisting of measurements of hematological, nephrological and hepatic parameters: CBC/platelets, blood ionogram, creatinine, albumin, transaminases (AST, ALT), alkaline phosphatases (ALP), total and conjugated bilirubin, PT, APTT, fibrinogen level
- Determination of lipase
- ACE and CA 19-9 assay
- KRAS status will be determined at each center but not routinely at inclusion
- **Fasting** sample for patients participating in the 'lipid' translational study; don't forget to perform it (according to the corresponding section, p25).

IV. INCLUSION

After the patient has signed the clinical consent form (Appendix 1) and the results of the examinations necessary for inclusion in the study have been verified, the patient can be included. For centers participating in the associated 'lipid' study, the specific information and consent form (Appendix 2) must be proposed.

[figure not shown]

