In all cases of treatment discontinuation, the patient remains in the analysis for intention-to-treat and overall survival, and for 30 days after the last study treatment for toxicity.

There is no exclusion period for a subsequent therapeutic trial.

IX. CENTRALIZED READING OF CT SCANS AND MRI

Responses will be evaluated according to RECIST version 1.1 criteria (Appendix 3) and will be reviewed by a panel of independent radiologists according to RECIST version 1.1 criteria and EASL criteria (Appendix 4).

Don't forget to keep the CDs and the report of the CT and MRI evaluation in the patient's file; the FFCD CRA will make a copy of these imaging assessments to centralize them at the CRGA on the 'FFCD Images' platform using a secure transmission via the company ETIAM.

X. MANAGEMENT OF SERIOUS ADVERSE EVENTS (SIA)

Safety will be assessed by evaluating the general, clinical and biological status of patients at the time of scheduled visits and by collecting events occurring between visits. Toxicities will be assessed using the NCI-CTC Toxicity Scale version 4.0 (Appendix 5).

X.1 Definitions

Adverse Event (AE)

An adverse event is a harmful occurrence in a person who is a subject of biomedical research, whether or not the occurrence is related to the research or the product being investigated. All adverse events will be recorded in the observation book on the pages provided.

Serious Adverse Event (SAE)

A serious adverse event is any event that meets at least one of the following criteria:

- Resulting in death,
- Life-threatening,
- Leading to hospitalization or prolonged hospitalization,
- Causing permanent disability or severe temporary incapacity,
- Causing a birth defect, fetal malformation or abortion,
- Medically significant (examples: overdoses, second cancers, pregnancies and new developments may be considered medically significant)

Pregnancy is an exclusion criterion in this trial.

However, if a pregnancy is discovered after inclusion, the patient must be excluded from the trial. The sponsor should be informed immediately via the Serious Adverse Event Reporting Form (no severity criteria should be checked). The patient should be followed until the outcome of the pregnancy and this outcome, whatever it may be, should be reported to the sponsor.

Hospitalizations included in the protocol will not be considered an SAE.

Undesirable Effect

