It will have to decide on the continuation of the study in light of the safety data. The sponsor may refer to it at any time in the event of significant events concerning the safety of the treatment. An analysis of SAEs is planned after the inclusion and intra-arterial treatment of the first 10 patients.

XII.6 Imaging Review Committee/Radiologist Panel

The anonymized copies of the evaluation reports will be centralized at the CRGA on the 'FFCD Images' platform using a secure transmission via the company ETIAM.

The RECIST version 1.1 and EASL responses will be reviewed by this panel of independent radiologists at a later date, who will confirm the responses and dates of tumor progression or recurrence once all study examinations have been retrieved.

XII.7 Steering Committee

A Steering Committee will be set up. It will be chaired by the study coordinator, [name] [name]. This committee will also include the president of the FFCD, the statistician of the FFCD and the president of the Biological Research Committee (if applicable). Its mission will be, among others, to take decisions related to the management of the research (amendment, premature closure if necessary, ...).

XII.8 14.2 Biological Research Committee

If it is decided to set up the collection of surgical parts relating to secondary hepatic resections, a Biological Research Committee will be established. Its mission will be to deal with problems related to the collection and banking of specimens and the organization of their analysis. The committee shall meet regularly and report its proposals to the Board of Directors. This committee will include the study coordinator and a biologist; the chairperson of this committee will be designated afterwards.

XIII. JUSTIFICATION OF THE TEST

The treatment of metastatic colorectal cancer has become more diverse in recent years. Several chemotherapy regimens and targeted therapies are available as first-line treatment. The majority of liver metastases are not immediately resectable (in about 85% of patients) and studies with different combinations indicate that aggressive first-line chemotherapy in initially inoperable patients can achieve complete resection of metastatic disease (1). It is therefore important to develop new therapeutic strategies in metastatic colorectal cancer.

Anti-tumor therapy

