7.4.3.1 Definition

It is defined as the relative difference between the sum of the largest diameters of RECIST target lesions at NADIR in the absence of new lesions or progression of non-target lesions and the sum of the largest diameters of RECIST target lesions at inclusion. It will be given according to the investigator and according to the centralized review of the images.

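### Local CT/MRI reports sit on the central-review platform with the images, the panel is asked to confirm responses and dates, and no rule keeps the local reading from the readers

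*Protocol*

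**What the plan says.** Protocol IX (Centralized reading of CT scans and MRI) provides for review by independent radiologists under RECIST 1.1 and EASL. It tells sites to "keep the CDs and the report of the CT and MRI evaluation" in the patient's file, and says that "the FFCD CRA will make a copy of these imaging assessments to centralize them at the CRGA" on the FFCD Images platform. Protocol III gives a similar instruction for the baseline radiology CDs: "the ARC FFCD will make a copy of these imaging studies".

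Protocol XII.6, the section on the radiologist panel, describes the centralized material differently: "The anonymized copies of the evaluation reports will be centralized at the CRGA", on the same platform. It says the RECIST and EASL responses will be reviewed by the panel, "who will confirm the responses and dates of tumor progression or recurrence once all study examinations have been retrieved".

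The SAP assigns EASL response to central review (7.4.2.1). For depth of response (7.4.3.1) it says "It will be given according to the investigator and according to the centralized review of the images", and it repeats that sentence for early tumor shrinkage (7.4.4.1). The primary endpoint (Protocol XII.2.1, SAP 7.3.1) and best RECIST response (SAP 7.4.1.1) are assessed by the investigator.

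**The concern.** The trial is open-label and non-randomized (SAP 4.1), and its primary endpoint rests on the investigator's reading. The panel is the only reading in the plan that could be independent of the treating teams. Giving a central value beside an investigator value is informative only if the central value was formed without the other in view.

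The procedure as written does not secure that. The local report goes to the platform that serves the central reading, the task is worded as confirmation, and nothing sets an order in which the panel reads first and sees local results afterwards. Anonymizing a report removes the patient's identity. It does not remove whatever the report contains of the local target lesions, diameter sums, response call or progression date. A reader who has seen these may select the same lesions, measure towards the same sums or accept the same date. The central figures would then be a weaker check on optimistic local reading than a reader of the results would assume.

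**Working it through.** The point rests on no figure in the plan, so the check is a comparison of the text.

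**1. What reaches the platform.** Protocol III covers the baseline CDs. Protocol IX covers the on-study CDs and the report, referred to together as imaging assessments. Protocol XII.6 names only the evaluation reports. Read together, both images and local reports are centralized.

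**2. What the panel is asked to do.** Under IX it reviews responses by RECIST 1.1 and EASL. Under XII.6 it confirms responses and progression dates once every examination has been collected. The SAP describes a central review of images that yields its own values. These descriptions are compatible only if confirming means reading the images afresh, and no section says so.

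**3. What keeps the readings apart.** No section of either document withholds local reports, lesion choices, responses or dates from the readers. None requires a locked central read, and none gives a number of readers or an adjudication rule.

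**4. How each result could be reached.**

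| Central result | Local counterpart | Route of influence |
|---|---|---|
| RECIST response, progression date | Investigator call and date | Direct: these are what XII.6 asks the panel to confirm |
| Depth of response (SAP 7.4.3) | Investigator value | Through sight of local target lesions and sums; not literally within the task of confirming |
| Early shrinkage, 20% and 30% thresholds (SAP 7.4.4) | Investigator value | As for depth of response |
| EASL response (SAP 7.4.2) | None described | Indirect only, through the local lesion choice or RECIST call |
| Primary endpoint, decision rule (SAP 7.3) | Investigator-assessed | None: the panel does not feed it |

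The most direct route concerns RECIST responses and dates, for which the SAP names no central-review analysis. The central results that the SAP does plan are the next three rows, where the influence is less direct.

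**5. Size.** The documents give no rate of agreement or disagreement between local and central readings, so the bias cannot be estimated. The only available arithmetic is the weight of one patient in a rate. SAP 7.4.4 leaves its population blank. If the denominator is the 48 evaluable patients, one patient crossing a shrinkage threshold moves the rate by 1/48 = 2.1 percentage points. If it is the 58 to be included, the figure is 1/58 = 1.7 points. This shows sensitivity. It does not estimate how many patients would cross.

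**The case against.** The strongest reply is that the plan already describes central reading of images. The CDs are copied at baseline and during the study, IX is headed as a reading of scans, the panel waits until all examinations are in, and the SAP refers to review of the images. XII.6 says the reports are centralized at the CRGA, which is the sponsor's data centre; it does not say the readers open them. The text is also visibly a translation (SAP 4.2 is partly still in French), so a reading procedure should not be built on the single words *reports* and *confirm*. Finally, the central results are secondary and descriptive, with no test and no comparator arm.

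Much of this stands. A reader might infer that the panel is sent the local reports, merely endorses them, and so produces results that are anchored on the local reading. The documents do not support that: they neither show the reports to the readers nor withhold them, and the images are centralized too. Nor do they support saying that reported agreement would be overstated, since no agreement analysis is planned, or that the central values offer no protection at all. For EASL there is no local conclusion to confirm.

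What the reply does not remove is the missing safeguard. Putting the reports on the platform and having no rule to withhold them do not depend on how one verb was translated. Following the written procedure exactly would permit a read that is not independent.

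**Conclusion.** The point holds as a risk that the procedure leaves open. Protocol IX and XII.6 put local reports alongside the images, word the panel's task as confirming responses and dates, and set no separation between the two readings. Central results may be influenced by the local reading by the routes tabulated above.

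The consequence is confined to secondary, descriptive central results. The 33-of-48 decision rule and the sample size are unaffected. That the local reading has in fact shaped the central values cannot be concluded from the documents. The conclusion assumes that readers with access to the platform could open the reports, and that a report may contain local lesions, sums, responses or dates. If a separate reading procedure already withholds them, the point reduces to bringing the protocol text into line with it. The change is worth making because it is cheap and protects the only reading in the plan that could be independent of the investigators.

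**What to change.** In Protocol IX and XII.6:

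- Give the panel the images only, and file the local reports where readers cannot open them.
- Have readers record and lock their own lesion selection, measurements, RECIST and EASL response, and progression date before any local report or investigator call is released.
- Replace *confirm* with *determine independently*, so that XII.6 agrees with the SAP's description of a central review of images.
- State the number of readers and how disagreements between them are settled.
- Make any comparison with local data only after the lock.

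The panel reads only once all examinations have been collected, so the rule can be put in place before reading starts. SAP 4.5 allows the analysis plan to be adjusted before database freeze if a matching sentence is wanted there.

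Separating the two readings needs no additional images or reads and no change of readers. The costs are separate storage of the reports, a lock step with controlled release afterwards, and readers working without the local report during the first read.

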XV.4 APPLICATION FOR AUTHORIZATION TO THE CPP AND AFSSAPS

This protocol has been authorized by the CPP (Comité de Protection des Personnes) Ile-de-France 8, on 14/01/2013 (appendix 11).

This protocol received a favorable opinion from the ANSM, Agence Nationale de Sécurité du Médicament et des Produits de Santé (formerly AFSSAPS) on 8/01/2013 (Appendix 12).

XV.5 COLLECTION OF THE PATIENT'S CONSENT

The investigator undertakes to collect, after information, the clinical and biological consent (if applicable) of the patient in writing; the information sheets and consent forms are in appendix 1 and 2. A copy of these consents must be kept by the investigator for 15 years. The original must be given to the patient.

XV.6 INFORMATION TO HOSPITAL MANAGEMENT AND RESEARCH AGREEMENT

Prior to the implementation of the study, the hospital management will be informed by the sponsor of the investigator's interest in participating in this trial.

A no-cost research agreement will be established between the investigating center administrator and the sponsor.

XV.7 DATA ARCHIVING

The files will remain confidential and can only be consulted under the responsibility of the doctors in charge of the patients. The sponsor and the health authorities in case of inspection will have direct access to these documents.

At the end of the trial, the observation book will be kept for 15 years by the investigator.

XV.8 IT SUPPORT

In accordance with the text of the law n° 78-17 of January 6, 1978 modified by the law of August 9, 2004, relating to data processing, files and freedoms, the data of the trial will be recorded in a data bank of the Center of Randomization and Management Analysis of the FFCD, with the exception of the elements relating to the identity of the patients.

XV.9 DATA PROCESSING

The FFCD's Center for Randomization Management and Analysis (CRGA) will be responsible for data management and analysis.

XV.10 MONITORING, QUALITY ASSURANCE AND INSPECTIONS BY AUTHORITIES

The investigator agrees in advance that the records of the patients included in the trial may be consulted by a person mandated by the FFCD and/or by the health authorities to carry out an audit. On-site monitoring of records, scheduled after agreement with the investigator, may take place during and after the trial inclusion period.

This protocol will be monitored by the FFCD's mobile ARCs.

The investigator agrees to sign the observation books at the end of each visit.

XVI. PUBLICATION

The current FFCD publication rules will be applied (Appendix 9)

3.1 Objectives of the study

3.1.1 Main objective

The primary objective of this study is to evaluate the progression-free survival rate (proportion of patients alive without progression) at 9 months after the start of treatment according to the RECIST 1.1 criteria, assessed by the investigator. The events to be considered will be progression or death.

3.1.2 Secondary objectives

The secondary objectives of the study are to evaluate:

- Tolerance to the treatment
- Best response according to RECIST v1.1 criteria (as determined by the investigator)
- Best response according to EASL criteria (evaluated in centralized review)
- Progression-free survival according to RECIST v1.1 criteria
- Progression-free survival
- Overall survival
- The rate of secondary resections
- Changes in tumor marker levels
- The maximum depth of response
- Early response rate (1^{ère} assessment at 8 weeks)

3.1.3 Exploratory studies

The objective is to search for predictive factors of progression-free survival and/or overall survival.

[figure not shown]
4 Experimental design

4.1 Scheme of the study

This is an open-label, non-randomized, multi-center Phase II trial.

[figure not shown]
4.2 Chronological sequence

- **Bilobar treatment in 2 sessions**

Après ce plan de traitement initial, tous les patients recevront une chimiothérapie par FOLFOX toutes les 2 semaines, selon le schéma habituel jusqu'à progression ou toxicité inacceptable.

- **Sequential unilobar treatment in 4 sessions**

Le traitement par chimio-embolisation, pourra, au choix de l'investigateur, être administré de manière unilobaire et séquentielle, en 4 séances. Ainsi, le foie droit et le foie gauche seront traités en alternance. Les administrations de DEBIRI seront alors réalisées à J17, J31, J45, J59 (\pm 2j), ou en cas de décalage de cure de chimiothérapie, 3j (\pm 2j) après C2, C3, C4 et C5 de FOLFOX. Après ce plan de traitement initial, tous les patients recevront une chimiothérapie par FOLFOX toutes les 2 semaines, selon le schéma habituel jusqu'à progression ou toxicité inacceptable.

4.3 Justification of the number of subjects needed

A 1-step Fleming design was used, with a one-sided α risk of 5% and a power ($1-\beta$) of 90%.

The clinical assumptions made were:

H_0 : A 55% progression-free live proportion during the first 9 months is unattractive;

H_1 : A proportion of patients alive without progression of more than 55% during the first 9 months would show the interest of the treatment; a proportion of 75% is hoped for.

48 evaluable patients were required. Taking into account a 20% rate of patients lost to follow-up or not evaluable, 58 patients were to be included.

The decision rules are as follows: of the 48 evaluable patients

- If 32 or fewer patients are alive without progression, then the treatment is considered ineffective
- If 33 or more patients are alive without progression, then the treatment is considered effective

The decision rule will be adjusted based on the actual number of evaluable patients.

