Study design and treatment plan	
Microbeads (100-300μm), loaded with irinotecan (DEBIRI). The maximum dose per procedure is 100 mg of irinotecan, combined with intravenous FOLFOX.
 
For patients with unilobar or bilobar liver involvement, DEBIRI will be injected at D17 and D45 (after the 2nd and 4th cycle of systemic chemotherapy with FOLFOX).
 
Patients with bilobar involvement but for whom the investigator decides that the treatment will be unilobar and sequential, there will be 4 sessions. Thus, the right and left livers will be treated alternately. The DEBIRI administrations will then be performed at D17, D31, D45, D59, or in case of a shift in chemotherapy treatment, after the 2^{ème}, 3^{ème}, 4^{ème} and 5^{ème} cycle of FOLFOX.
 
FOLFOX will be administered every 2 weeks until progression or unacceptable toxicity.

Statistical methods	
A 1-step Fleming design will be used, with a one-sided α risk of 5% and a power (1-β) of 90%.
 
The assumptions are:
 
 • H0: A proportion of patients living without progression of 55% during the first 9 months is uninteresting; • H1: A proportion of patients living without progression of more than 55% during the first 9 months would show the interest of the treatment; a proportion of 75% is hoped for.

	
Total number: 48 evaluable patients
 
Taking into account a 20% rate of lost to follow-up or non-evaluable patients, 58 patients should be included.
 
At the end of recruitment:
 
During analysis:
 
 - if 32 or fewer patients are alive without progression, then the treatment is considered ineffective - if 33 or more patients are alive without progression, then the treatment is considered effective 
The decision rule will be adjusted based on the actual number of evaluable patients.

Number of subjects needed	58
Associated translational studies	
 - On lipid parameters: The objective of this study will be to evaluate the impact of the different parameters of the lipid profile and the metabolism of lipoproteins on the response to treatment. - On Pathology: At the end of the study, if a sufficient number of patients have undergone secondary resections of liver metastases, a collection of surgical parts will be organized. An anatomopathological study of the tumor parenchyma and the healthy parenchyma resected after DEBIRI treatment will be performed.

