The primary endpoint will be the proportion of patients alive without progression (death will be considered as progression) at 9 months after the start of treatment according to RECIST V1.1 criteria, as assessed by the investigator.

Progression-free survival time will be defined as the time interval between the date of inclusion and the date of progression or death (regardless of cause). For patients alive without progression, the time interval between the date of inclusion and the date of last morphological evaluation will be taken.

XII.2.2 Secondary Criteria

The secondary endpoints will be:

- Tolerance to the treatment
- Response rate according to RECIST v1.1 criteria at 9 months (according to the investigator)
- Response rate according to EASL criteria (assessed by centralized review) at 9 months
- Hepatic progression-free survival according to RECIST v1.1 criteria at 9 months
- Overall survival
- Progression-free survival
- The rate of secondary resections
- Changes in tumor marker levels

Liver progression-free survival will be defined as the time interval between the date of inclusion and the date of liver progression as assessed by the investigator's RECIST V1.1 criteria or death (regardless of cause) or the date of the last morphological assessment for patients alive without progression.

Overall survival will be defined as the time interval between the date of inclusion and the date of death regardless of the cause of death or the date of last news for living patients.

Tolerance to treatment will be assessed by:

- duration of treatment, doses received, dose reductions and deferrals
- Toxicities collected at each monthly visit, and described according to NCI-CTC version 4.0 criteria; Grade 3, Grade 4 and Grade 5 toxicities will be reviewed
- the number and description of SAEs

Changes in tumor marker levels (CEA and CA 19-9) will be assessed throughout the study.

XII.3 Calculation of the number of subjects needed

A 1-step Fleming design will be used, with a one-sided α risk of 5% and a power (1- β) of 90%.

The assumptions are:

- H0: A proportion of patients living without progression of 55% during the first 9 months is uninteresting;
- H1: A proportion of patients living without progression of more than 55% during the first 9 months would show the interest of the treatment; a proportion of 75% is hoped for.

Total number: **48 evaluable patients**

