Taking into account a rate of 20% of patients lost to follow-up or not evaluable, **58 patients should be included**.

At the end of recruitment:

During analysis:

- if 32 or fewer patients are alive without progression, then the treatment is considered ineffective
- if 33 or more patients are alive without progression, then the treatment is considered effective

The decision rule will be adjusted based on the actual number of evaluable patients.

XII.4 Statistical analysis plan

Analysis Populations:

Patients included in the study will be described on an intention-to-treat (ITT) basis as well as patients not evaluable for the primary endpoint.

A patient is considered evaluable if he or she has had chemoembolization and received at least one cycle of chemotherapy and for whom we have at least one evaluation during the 9 months of follow-up.

All efficacy analyses will be performed on a modified intention-to-treat basis (evaluable patients) included in the study regardless of eligibility criteria and treatment received.

Tolerability population: the ITT population that received at least one dose of the treatments.

In all cases of discontinuation, the patient remains in the intention-to-treat analysis. There is no exclusion period for a subsequent therapeutic trial.

Key analyses:

A statistical analysis plan will be written prior to freezing the database.

The description of clinical and medical variables will be done using percentages (95% confidence interval) for qualitative variables and mean (standard deviation) and median (Min-Max) as well as inter-quartile range (Q1-Q3) for quantitative analysis.

Survivals and times will be estimated by the Kaplan Meier (KM) method. They will be described by medians and rates at different time points with their 95% confidence intervals.

Median follow-up time will be calculated using the reverse Kaplan Meir method.

The time to onset of grade 3/4/5 toxicity will be estimated using the Kaplan Meier method.

Exploratory Analyses:

- research into factors predictive of progression-free survival and/or overall survival

XII.5 Independent Committee Supervisory Committee

An independent committee composed of 1 clinician / 1 methodologist / 1 pharmacovigilant expert will be formed before the start of the trial.

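### The design does not deliver its stated 90% power: the 33-of-48 rule has exact power 87.7%, and 58 inclusions do not cover a 20% loss

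*SAP*

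**What the plan says.** The protocol synopsis, protocol XII.3 and SAP 4.3 give the same design. The protocol specifies a single-stage Fleming design with "a one-sided α risk of 5% and a power (1-β) of 90"%. The null hypothesis in SAP 4.3 is "A 55% progression-free live proportion during the first 9 months is unattractive"; for the alternative, "a proportion of 75% is hoped for". All three places require 48 evaluable patients, and the success rule in the protocol is "if 33 or more patients are alive without progression, then the treatment is considered effective".

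For enrolment the synopsis says "Taking into account a 20% rate of lost to follow-up or non-evaluable patients, 58 patients should be included", and SAP 4.3 repeats it: "Taking into account a 20% rate of patients lost to follow-up or not evaluable, 58 patients were to be included".

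The rule is to be adapted if the evaluable number is not 48 (protocol XII.3, SAP 4.3 and 7.3.2), but no method or table of cut-offs is given. Under SAP 5.1.2 and 7.3.2 the primary analysis uses evaluable patients only: those who had chemoembolization, at least one chemotherapy cycle and at least one assessment in the 9 months. Patients who are not evaluable therefore leave the denominator. SAP 7.3.2 calls for an exact one-sided 95% interval. Neither document says that the 90% is approximate.

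**The concern.** Two separate planning figures are affected. The first is the power of the written rule. A cut-off on a binomial count has an exact power, and for 33 of 48 it is below the stated 90%. The second is the allowance for loss. Multiplying 48 by 1.20 does not compensate for losing 20% of those enrolled, because the loss applies to the larger number.

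The trial ends in a two-way verdict, effective or ineffective. Anyone reading a negative verdict will take the chance of wrongly rejecting a treatment with a true 75% rate to be 10%. If it is higher, a negative result is weaker evidence than the documents imply.

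**Working it through.** **Inputs** (protocol XII.3, SAP 4.3): p0 = 0.55, p1 = 0.75, one-sided alpha 0.05, power 0.90, n = 48 evaluable, success at ≥33, loss 20%, 58 included. Write X for the number alive without progression, X ~ Bin(n, p).

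**1. Reproducing the plan's figures.** Fleming's normal approximation is

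n = [(z₀.₉₅√(p0(1−p0)) + z₀.₉₀√(p1(1−p1))) / (p1−p0)]² = [(1.645√0.2475 + 1.282√0.1875) / 0.20]² = 47.1, hence 48.

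The cut-off is the nearest integer to 48 × 0.55 + 1.645√(48 × 0.55 × 0.45) = 32.07, plus 1, which is 33. The approximate power at n = 48 is Φ[(0.20 − 1.645√(0.2475/48)) / √(0.1875/48)] = 90.5%. So 48, 33 and 90% all follow from the named method.

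**2. Exact properties at n = 48.**

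| Rule | P(success given 0.55) | P(success given 0.75) |
|---|---|---|
| ≥33 of 48 | 3.69% | 87.7% |
| ≥32 of 48 | 6.83% | 93.0% |

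No cut-off at 48 gives both alpha ≤5% and power ≥90%. The smallest exact design that does is 50 evaluable with ≥34 (alpha 4.27%, power 90.2%).

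**3. Loss allowance.**

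- The plan's figure: 48 × 1.20 = 57.6, rounded up to 58.
- Needed for a 20% loss: 48/0.80 = 60.
- Evaluable out of 58 at 20% loss: 58 × 0.80 = 46.4, about 46.
- Loss that 58 can absorb: 1 − 48/58 = 17.2%.
- Chance of at least 48 evaluable out of 58 with independent 20% loss: P(Bin(58, 0.80) ≥ 48) = 37%.

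**4. Power at the planned loss.** The documents give no cut-off for 46. Fleming's formula (nearest integer to 30.85, plus 1) and the exact alpha ≤5% rule both give 32. A cut-off of 31 would have alpha 6.03%. Because the count is discrete, power does not rise steadily with n:

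| Evaluable | Exact cut-off | Alpha | Power |
|---|---|---|---|
| 45 | 31 | 4.09% | 86.7% |
| 46 | 32 | 3.16% | 84.7% |
| 47 | 32 | 4.74% | 89.4% |
| 48 | 33 | 3.69% | 87.7% |
| 49 | 34 | 2.86% | 85.8% |
| 50 | 34 | 4.27% | 90.2% |

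Averaging over the evaluable number as Bin(58, 0.80), with the cut-off reset each time to keep exact alpha ≤5%, gives power 86.1%. From 60 inclusions the same average is 87.4%.

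**The case against.** The strongest reply is that the first half is not a miscalculation. The documents name Fleming's design, and its approximation returns 48, 33 and 90.5%. The distance to 87.7% is the usual gap between a normal approximation and a discrete count. This is correct about how the figure arose, but it does not make 90% the power of the written rule. The SAP also works on the exact scale for the primary interval, where the one-sided 95% lower bound is 56.0% at 33/48 and 53.9% at 32/48. The interval and the cut-off thus agree, and exact power is the relevant one.

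A second reply is that 84.7% is a low point between better neighbours: 45 evaluable gives 86.7% and 47 gives 89.4%. That stands. Although 46 is the expected number at the planned loss, the 86% average is the steadier summary.

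Third, 58 instead of 60 is only two patients and changes average power by about 1.2 points (86.1% against 87.4%). That also stands: most of the shortfall comes from the approximation. The slip is nevertheless plain arithmetic and depends on no approximation.

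Fourth, the documents already foresee adjusting the rule, and exact alpha stays below 5% under either method of setting the cut-off. This protects against a false positive but does not restore power.

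**Conclusion.** The concern holds. The exact power of the written rule is 87.7%, which is 2.3 points below the stated figure. At the loss rate the plan itself assumes, it is 84.7% with exactly 46 evaluable, and about 86% averaged over the random number evaluable. The false-negative risk at a true rate of 75% is therefore about 12% at 48 evaluable, 14% on average and 15% at 46, against the stated 10%. The 58 inclusions cover a loss of 17.2%, not 20%.

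The size is modest, and only power is affected. The estimate and its exact interval are untouched. The figures assume a true rate of 75%. Those below 48 evaluable also assume a cut-off reset to keep exact alpha at or below 5%, and the averaged figure assumes that loss is independent between patients and unrelated to outcome.

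**What to change.** Restate the design in the protocol synopsis, protocol XII.3 and SAP 4.3, for example: *With 48 evaluable patients and success at 33 or more, the exact one-sided alpha is 3.7% and the power at 75% is 87.7%. The 58 inclusions allow for 17% non-evaluable patients; at 20% (46 evaluable, success at 32 or more) the power is 84.7%.* The average of about 86% can be added, since power at a single n depends on where the cut-off falls.

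Separately, define the adjusted cut-off in SAP 4.3 and 7.3.2 as the smallest r with exact P(X ≥ r | n, 0.55) ≤ 5%. This returns 33 at n = 48. It is a specification and not just a correction, because it can differ from Fleming's formula: at 52 evaluable it gives 35 against 36, and at 57 it gives 38 against 39. It should therefore be fixed before outcomes are known, and SAP 4.5 in any case requires changes before the database freeze.

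Correcting the power and loss figures is a change of wording with no extra enrolment; its price is a slightly less favourable power. If the sponsor instead wanted a true 90%, 50 evaluable patients would be needed, or 50/0.80 = 62.5, so 63 inclusions at 20% loss. The correction does not require this.
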